### **3.3 Primary Safety Endpoints**

$\omega$ 3 FFAs have an excellent safety and tolerability profile. Most common side effects associated with their use in human trials include diarrhea, indigestion, nausea, fishy taste and belching. Total incidence of GI disturbances in phase 2 and 3 clinical trials has varied between 1.4 – 4.9%, with a very low rate of study termination [27]. The rate of study withdrawal was 3.4% in a phase 3 study using EPA [20].

We will specifically assess the prevalence of adverse effects in subjects randomized to drug or placebo. Adverse effects which have been reported in the literature, may include:

1. Gastrointestinal adverse effects such as: abdominal pain, nausea, vomiting, diarrhea.
2. Altered (fishy) taste in the mouth. The preparation used in this trial using orange oil to mask this effect.
3. Allergic reactions.
4.  $\omega$ 3 FFAs have antiplatelet activity, however increased rates of bleeding have not been seen in large clinical cardiovascular trials [28]. We will specifically assess rates of any mucosal or skin bleeds in monthly telephone calls (1,2,3,4,5 months) and at the 6 month visit.

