#### 4.3 **Subject Recruitment, Enrollment and Screening**

Subjects between 18-85 years of age, with known BE (no dysplasia and low-grade dysplasia) will be identified using an existing GI database for participation in this study. Invitation letters will be mailed to eligible subjects. Subjects will be called to discuss study and scheduled for a screening visit. Subjects taking  $\omega$ 3 FFA as a supplement will discontinue use at least four weeks prior to visit 1. Subjects will report fasting 12 hours for this visit. Subjects meeting inclusion and exclusion criteria will be screened and consented. Baseline assessment will include the measurement of height, weight, waist circumference, hip circumference and waist/hip ratio using standard methods of anthropometric measurements. A comprehensive medication list will be obtained. Patients will also fill out the Reflux Symptom Questionnaire (RSQ)/GER Questionnaire a validated instrument to assess reflux symptoms All patients will continue their baseline PPI regimen to control gastroesophageal reflux. 20cc of blood will be drawn after 12 hours of fasting to obtain a baseline serum FFA profile . Clinical baseline blood will be drawn for inclusion/exclusion: INR, LDL, AST and ALT. Endoscopy will then be performed in a standard manner. Six biopsies will be obtained from the GE junction, and seven biopsies from the BE mucosa 1 cm above the GE junction. Two biopsies from each site will be formalin fixed and paraffin embedded (for inflammatory score assessment) and the remainder frozen at  $-80$  C for subsequent analysis. An additional seven biopsies will be obtained from the squamous mucosa at least 3 cm above the proximal end of the BE segment. Two will be placed in formalin (or other fixative) and paraffin embedded (IHC for macrophage cell counts) and the remainder will be snap frozen at  $-80^{\circ}$  C (PGE2 levels). Endoscopic brushings of the Barrett's segment as well as squamous tissue will be obtained and frozen for each subject. Endoscopic mucosal impedance measurement will be completed during endoscopy. A single slice CT scan of the

abdomen will also be obtained at baseline for each subject to quantify visceral and subcutaneous fat area in the abdomen.

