#### **5.4 Subject Compliance Monitoring**

Phone calls will be made by the study coordinator every month to the patients to assess for any adverse effects (presence and grade) and reinforce compliance. Compliance will also be assessed by pill counts during this telephone call. Adverse effects mentioned in section 3.3 will be specifically assessed in the phone calls (see phone call script).

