**6.2 Visit 2**

Subjects will undergo repeat assessment at six months following randomization. This will include anthropometry (similar to baseline), a fasting blood draw and endoscopy with research biopsies and brushings as outlined at baseline. Subjects will also fill out the Reflux Symptom Questionnaire (RSQ)/GER Questionnaire. Remaining medication will be counted and recorded.

If the participant is to be scheduled for a clinically indicated upper endoscopy and procedures that are ordered cannot be done on the Clinical Research Unit, (i.e. radiofrequency ablation, endoscopic mucosal resection, esophageal dilation, endoscopic ultrasound) the research portion of the procedure will be done during the clinically indicated upper endoscopy. These research procedures will include biopsies and brushings of the esophagus as well as mucosal impedance.

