**Schedule of Events**

Study Activity	Month 0	Month 1	Month 2	Month 3	Month 4	Month 5	Month 6	Month 6 + 7 days
Informed consent	X							
History	X							
Concurrent meds	X							
Physical exam (ht, wt, hip/waist, VS)	X						X	
Blood draw (FFA, LDL, AST, ALT) INR )	X						X	
Endoscopy with bx/brushing and mucosal impedance measurement	X						X	
Randomization	X							
Adverse event evaluation		X	X	X	X	X	X	X
Pill count		X	X	X	X	X	X	
Single slice CT scan of abdomen	X							
Questionnaire	X						X	

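### The solicited safety effects have no scheduled pre-dose inquiry and no new-or-worse rule, so background symptoms and biopsy effects enter both arms and blur the comparison

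*Combined protocol and SAP*

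**What the plan says.** Section 3.3 (Primary Safety Endpoints) states the measure: "We will specifically assess the prevalence of adverse effects in subjects randomized to drug or placebo". The listed effects begin with "Gastrointestinal adverse effects such as: abdominal pain, nausea, vomiting, diarrhea" and go on to altered taste, allergic reactions and bleeding. For bleeding, the timing is given: "We will specifically assess rates of any mucosal or skin bleeds in monthly telephone calls (1,2,3,4,5 months) and at the 6 month visit". Section 5.4 places the rest in the monthly calls: "Adverse effects mentioned in section 3.3 will be specifically assessed in the phone calls (see phone call script".

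In the Schedule of Events, the row "Adverse event evaluation" is marked at Months 1 to 6 and at Month 6 + 7 days. Month 0 is blank.

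Visit 1 (sections 4.3 and 6.1) covers a brief gastroenterology consultation, anthropometry, a medication list, a reflux questionnaire, blood tests, endoscopy and a CT slice. The schedule adds a History item, whose content is not described. No inquiry about the section 3.3 effects is listed.

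At the same visit, section 4.3 specifies "Six biopsies will be obtained from the GE junction, and seven biopsies from the BE mucosa 1 cm above the GE junction" and then "An additional seven biopsies will be obtained from the squamous mucosa". Section 6.1 goes on, in the same visit description, to randomization and the first supply of study medication. Section 6.2 repeats the procedure at six months: "a fasting blood draw and endoscopy with research biopsies and brushings as outlined at baseline".

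Section 8 grades the attribution of events to the protocol, on a scale from unrelated to definitely related. Section 7 contains no safety analysis.

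**The concern.** A prevalence counts everyone who has the symptom, whenever it began. Without a pre-dose answer to the same questions, the planned data offer no scheduled way to separate a continuing symptom from a new one. The first call also looks back over a period that opens with both an endoscopy with biopsies and the start of study medication.

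Three things are at stake:

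- **The arm comparison.** Background symptoms add variance to both arms. They also leave fewer patients in whom a drug effect could show as a new symptom.
- **The single-arm figure.** Section 3.3 quotes an incidence of GI disturbances of 1.4% to 4.9% from other trials. A prevalence that includes pre-existing symptoms is a different quantity and cannot be set against it.
- **Judgements on single patients.** Randomization does not help in deciding whether one patient's symptom is related. The scale in section 8 refers to the protocol as a whole, so it does not separate study drug from endoscopy and biopsy.

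The pilot is meant to inform a larger trial, and tolerability figures mixed with background symptoms serve that purpose poorly.

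**Working it through.** The plan gives no safety calculation, so there is no figure of its own to reproduce.

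**1. Biopsies at Visit 1** (section 4.3): 6 (GE junction) + 7 (Barrett's mucosa) + 7 (squamous mucosa) = 20.

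**2. Inputs for the illustration**

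- 40 per arm, from section 3.1. Section 7.1 allows up to 90 randomized, or 45 per arm.
- GI disturbance rate of 1.4% to 4.9%, from section 3.3. Treating it as an excess over placebo is an assumption, because the text gives it as a total incidence.
- Pre-existing prevalence *b*: not in the documents; assumed 10%, 20% or 30%.
- New-onset background when only new or worsened symptoms count: assumed 2%.

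**3. Precision.** With placebo proportion *b* and drug proportion *b* + 0.049:

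half-width = 1.96 × √{[(b + 0.049)(1 − b − 0.049) + b(1 − b)] / n}

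| What is counted | b | Sum in square brackets | Half-width, n = 40 | Half-width, n = 45 |
|---|---|---|---|---|
| All symptoms | 0.10 | 0.149×0.851 + 0.10×0.90 = 0.2168 | 14.4 points | 13.6 points |
| All symptoms | 0.20 | 0.249×0.751 + 0.20×0.80 = 0.3470 | 18.3 points | 17.2 points |
| All symptoms | 0.30 | 0.349×0.651 + 0.30×0.70 = 0.4372 | 20.5 points | 19.3 points |
| New or worsened only | 0.02 | 0.069×0.931 + 0.02×0.98 = 0.0838 | 9.0 points | 8.5 points |

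The first three rows leave out the 2% new-onset background that the last row includes. Adding it makes the placebo proportion 1 − (1 − b)(0.98) = 0.118, 0.216 or 0.314. The half-widths at 40 per arm then become 15.3, 18.7 and 20.7 points. The comparison barely changes, and the omission was not in the concern's favour.

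**4. Dilution.** The formula above holds the difference at 4.9 points, so it shows no dilution. For that, let *r* be the drug-caused rate, acting independently of a persisting background *b*:

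drug-arm prevalence = 1 − (1 − b)(1 − r); difference = r(1 − b)

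- b = 10%: the drug arm expects 4.5 (r = 1.4%) to 5.8 (r = 4.9%) of 40, placebo 4.0 of 40.
- b = 30%: the drug arm expects 12.4 to 13.4 of 40, placebo 12.0 of 40. The difference falls from 1.4–4.9 points to 0.014 × 0.7 = 1.0 and 0.049 × 0.7 = 3.4 points.
- Background accounts for 12.0/13.4 = 90% to 12.0/12.4 = 97% of drug-arm cases at b = 30%.

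In this model the difference shrinks; it is never inflated.

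**The case against.** **A reader might infer that these symptoms are counted as drug effects.** The documents do not support that. Section 3.3 compares drug with placebo, patients and investigators are blinded (section 5.3), and section 8 offers an unrelated grade. Background symptoms and biopsies fall on both randomized arms, so the contrast is not pushed towards harm. This objection stands. One qualification applies. Section 8 counts expected effects as adverse events only if serious, so it is unclear whether the non-serious effects solicited under section 3.3 are graded for attribution at all. Those passages must be reconciled.

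**A reader might infer that old and new symptoms can never be told apart.** That is not shown either. The phone-call script, the case report form and the content of the Month 0 History are not in the documents, and any of them might ask about onset. Even so, the endpoint has no rule for using such answers.

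**A high background rate is assumed.** True. Frequent reflux symptoms and esophagitis are excluded, as are the listed anticoagulant therapies, so the rate may be low. The described questionnaire and the symptom exclusion concern reflux, however, not the listed effects. Section 7 also anticipates aspirin and NSAID use.

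**Even 9 points exceeds a 4.9-point effect, and no safety test is planned.** Also true. The change does not make the pilot able to resolve an effect of that size; it makes the estimate tighter and interpretable.

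**A checklist before endoscopy cannot identify biopsy effects.** Correct; those need onset dates.

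**Conclusion.** The gap is real and worth closing. No pre-dose inquiry for the section 3.3 effects is scheduled, the endpoint has no new-or-worse rule, and attribution to the protocol does not separate drug from procedure. The consequences are a diluted and less precise arm contrast, and within-arm prevalences that cannot be read as drug effects or set against the quoted incidence. There is no bias towards drug harm, and the primary PGE2 estimate is untouched.

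At 40 per arm the illustrative loss is a half-width of about 14 to 20 points against about 9. This rests on an assumed 10% to 30% background, an assumed 2% new-onset rate, and reading 4.9% as an excess over placebo. With little background the loss would be small. The case for change does not depend on the exact size, because pre-dose status cannot be reliably reconstructed once treatment has begun.

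**What to change.** - **Schedule of Events:** mark adverse event evaluation at Month 0, and give the existing phone-call checklist at Visit 1 before endoscopy and first dose.
- **Section 3.3:** report, by arm, the proportion of patients with each solicited effect new or worse than that baseline. The word worse matters: counting only new symptoms would miss a drug effect in patients who already had the symptom.
- **Onset dates:** record them for every reported effect, so that events soon after the baseline and month 6 endoscopies can be shown separately. The month 6 biopsies are followed by the Month 6 + 7 days evaluation, so the procedure question arises there too. The baseline checklist alone does not remove biopsy effects.

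The cost is a few minutes per patient at Visit 1, one mark in the schedule, a short addition to section 3.3 and slightly more analysis work.

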## **4 Subject Selection Enrollment and Withdrawal**

Male and female patients between 18-85 years of age, with known BE (no dysplasia and low-grade dysplasia) will be identified using an existing GI database for participation in this study.

#### 4.1 **Inclusion Criteria**

- Presence of BE defined as  $\geq 1$  cm of visible columnar mucosa in the distal esophagus with intestinal metaplasia on histology.
- Absence of high grade dysplasia or EAC on baseline histology.
- BMI  $> 30$  kg/m^2 (this has been shown to correlate strongly with increased abdominal visceral fat)[26] or Waist circumference  $> 102$  cm in men,  $> 88$  cm in women.
- Ability to give informed consent.

#### 4.2 **Exclusion Criteria**

- Allergy to  $\omega$ 3 FFAs, fish or shellfish.
- Presence of high grade dysplasia or cancer on histology.
- Pregnant and or breastfeeding women
- Presence of esophagitis on initial endoscopy or symptoms of refractory GERD (heartburn or regurgitation  $\geq 2$  times a week) indicative of uncontrolled gastroesophageal reflux.
- Inability to give informed consent.
- Currently taking  $\omega$ 3 FFA as prescription.
- Anti-coagulant therapy (Plavix, Warfarin, Coumadin)
- AST or ALT level  $>$  three times upper limit of normal at baseline
- LDL  $> 200$  mg/dl at baseline.
- INR  $> 2$

#### 4.3 **Subject Recruitment, Enrollment and Screening**

Subjects between 18-85 years of age, with known BE (no dysplasia and low-grade dysplasia) will be identified using an existing GI database for participation in this study. Invitation letters will be mailed to eligible subjects. Subjects will be called to discuss study and scheduled for a screening visit. Subjects taking  $\omega$ 3 FFA as a supplement will discontinue use at least four weeks prior to visit 1. Subjects will report fasting 12 hours for this visit. Subjects meeting inclusion and exclusion criteria will be screened and consented. Baseline assessment will include the measurement of height, weight, waist circumference, hip circumference and waist/hip ratio using standard methods of anthropometric measurements. A comprehensive medication list will be obtained. Patients will also fill out the Reflux Symptom Questionnaire (RSQ)/GER Questionnaire a validated instrument to assess reflux symptoms All patients will continue their baseline PPI regimen to control gastroesophageal reflux. 20cc of blood will be drawn after 12 hours of fasting to obtain a baseline serum FFA profile . Clinical baseline blood will be drawn for inclusion/exclusion: INR, LDL, AST and ALT. Endoscopy will then be performed in a standard manner. Six biopsies will be obtained from the GE junction, and seven biopsies from the BE mucosa 1 cm above the GE junction. Two biopsies from each site will be formalin fixed and paraffin embedded (for inflammatory score assessment) and the remainder frozen at  $-80$  C for subsequent analysis. An additional seven biopsies will be obtained from the squamous mucosa at least 3 cm above the proximal end of the BE segment. Two will be placed in formalin (or other fixative) and paraffin embedded (IHC for macrophage cell counts) and the remainder will be snap frozen at  $-80^{\circ}$  C (PGE2 levels). Endoscopic brushings of the Barrett's segment as well as squamous tissue will be obtained and frozen for each subject. Endoscopic mucosal impedance measurement will be completed during endoscopy. A single slice CT scan of the

abdomen will also be obtained at baseline for each subject to quantify visceral and subcutaneous fat area in the abdomen.

Patients will be randomized to either a  $\omega$ 3 FFA preparation or a matching placebo for *six months*. A randomization schedule will be generated in the Division of Biomedical Statistics and Informatics and sent to the research pharmacy. Investigators and patients will be blinded to drug versus placebo assignment and only research pharmacy personnel and statisticians will have access to the assignments until the study is completed. Medications (drug and matching placebo) will be dispensed through the Mayo research pharmacy. Phone calls will be made by the study coordinator every month to the patients to assess for any adverse effects (presence and grade) and reinforce compliance. Compliance will also be assessed by pill counts during monthly call.

Patients will undergo repeat assessment at six months following randomization. This will include anthropometry (similar to baseline), a fasting blood draw for serum FFA profile, LDL, AST, ALT, INR and endoscopy with research biopsies as outlined at baseline. Subjects will also fill out the Reflux Symptom Questionnaire (RSQ)/GER Questionnaire. Investigators and patients will be blinded to drug versus placebo assignment. Both endoscopic procedures will be conducted in the outpatient CTSA unit on Charlton 7.

## **5 Study Drug**

### **5.1 Description**

#### *Drug and placebo:*

The DHA/EPA and placebo softgels will be supplied by Sancilio and Company, Inc. (Riviera Beach, FL) and stored in the Mayo Clinic Research Pharmacy at room temperature. Active drug will consist of 1200 mg of a  $\omega$ 3 FFA preparation containing 675 mg EPA and 300 mg DHA. Patients randomized to active drug will be placed on 3 capsules a day of this preparation. A matching placebo (1200 mg of ethyl oleate 3 capsules a day) will be provided to subjects randomized to placebo. Both preparations will contain orange oil to mask the gustatory effect of fish oils. Both drug and placebo will be provided by Sancilio & Company

### **5.2 Treatment Regimen**

Investigators, patients and statisticians will be blinded to drug versus placebo assignment. Patients randomized to active drug will be placed on 3 capsules a day of this preparation taken orally for six months. A matching placebo (1200 mg of ethyl oleate 3 capsules a day) will be provided to subjects randomized to placebo taken orally for six months. Both groups will take 2 capsules with breakfast and 1 capsule with their evening meal.

### **5.3 Method for Assigning Subjects to Treatment Groups**

A randomization schedule will be generated in the Division of Biomedical Statistics and Informatics and sent to the research pharmacy. Investigators and patients will be blinded to drug versus placebo assignment and only research pharmacy personnel and statisticians will have access to the assignments until the study is completed. Medications (drug and matching placebo) will be dispensed through the Mayo research pharmacy.

#### **5.4 Subject Compliance Monitoring**

Phone calls will be made by the study coordinator every month to the patients to assess for any adverse effects (presence and grade) and reinforce compliance. Compliance will also be assessed by pill counts during this telephone call. Adverse effects mentioned in section 3.3 will be specifically assessed in the phone calls (see phone call script).

#### **5.5 Prior and Concomitant Therapy**

A complete list of medications which the patient is currently consuming (both prescription and over the counter) will be obtained at the baseline visit.

Patients currently taking  $\omega$ 3 FFA s as prescription medications will be excluded from the study.

#### **5.6 Receiving, Storage, Dispensing and Return**

The research pharmacy will maintain the double-blind status of the study until all of the main outcomes have been measured. The DHA/EPA and placebo softgels will be supplied by Sancilio and Company, Inc. (Riviera Beach, FL) and stored in the Mayo Clinic Research Pharmacy at room temperature. The research pharmacy will assign participants to treatment or placebo based on a randomization table prepared by a statistician. Each participant will be instructed to swallow 2 softgels in the morning and 1 in the evening with meals (morning and evening) for a total of 3 softgels per day. The DHA/EPA softgels will each contain 1200mg of DHA/EPA for a total daily dosage of 3.6g/day. The placebo softgel will contain 1200mg of oleate. The pharmacy will maintain records of receipt, dispensation, and return pill counts for compliance.

At the completion of the study, there will be a final reconciliation of drug shipped, drug dispensed, drug returns, and drug remaining. This reconciliation will be logged on the drug reconciliation form, signed and dated. Any discrepancies noted will be documented and investigated, prior to return or destruction of unused study drug. Drug destroyed on site will be documented in the study files.

## **6 Study Procedures**

### **6.1 Visit 1**

Subjects taking  $\omega$ 3 FFA as a supplement will discontinue use at least four weeks prior to visit 1. Subjects will report fasting 12 hours to the Charlton CRU and have a brief consultation with a gastroenterologist specializing in Barrett's esophagus. Baseline assessment will include the measurement of height, weight, waist circumference, hip circumference and waist/hip ratio using standard methods of anthropometric measurements. A comprehensive medication list will be obtained. Subjects will also fill out the Reflux Symptom Questionnaire (RSQ)/GER Questionnaire a validated instrument to assess reflux symptoms. All subjects will continue their baseline PPI regimen to control gastroesophageal reflux. 20cc of blood will be drawn after 12 hours of fasting to obtain a baseline serum FFA profile. Clinical baseline blood will be drawn for inclusion/exclusion: INR, LDL, AST and ALT. Endoscopy will then be performed in a standard manner. Brushings will be obtained from the Barrett's segment as well as squamous tissue. Biopsies will be obtained from the GE junction, from the BE mucosa 1 cm above the GE junction and from the squamous mucosa 3cm above the proximal Barrett's segment. Endoscopic mucosal impedance measurement will be completed as described in the methods section above. A single slice CT scan of the abdomen will also be obtained at baseline for each subject.

Subjects will be randomized to either a  $\omega$ 3 FFA preparation or a matching placebo for *six months*. A 3 month supply of study medication will be given to subjects at randomization. Telephone calls will be made by the study coordinator every month to the subjects to assess for any adverse effects (presence and grade) and reinforce compliance. Compliance will also be assessed by pill counts during this call. An additional 3 month supply of study medication will be mailed to subject by research pharmacy after the 2 month telephone call.

